3.4.2. SUBJECT IDENTIFICATION

To maintain confidentiality, the subject's name should not be recorded on any study document other than the informed consent form. All subjects that give informed consent (sign the informed consent form) will be assigned a unique identifier in the following format: XX-YY-ZZZ. XX is the 2 digit assigned site number, YY is the sequential subject ID number, and ZZZ are the subject initials (initials of first name/middle name (if applicable)/last name). For example, the first subject named John Simon Doe at site 11 will be assigned 11-01-JSD.

3.4.3. SCREENING (DAY -60 TO DAY 0)

Prior to full screening, subjects will give informed consent and then be initially screened using the VAS, the Symptoms portion of the BPNS and the MNSI. Only subjects with a VAS score of $\geq 40 \text{ mm}$, a ≤ 5 point difference in symptom of BPNS between legs and MNSI score of ≥ 3 will be allowed to proceed with the full screening procedures.

If the VAS, BPNS and MNSI criteria are met, the rest of screening will proceed. If applicable, the subject will be washed out of prohibited medications. During medication wash-out and prior to randomization, subject eligibility will be assessed as follows:

- Evaluation of Eligibility Criteria
- Complete Medical History
- Concomitant Medications
- Vital Signs, including height
- Complete Physical Exam,
- EKG
- HbA1c
- Serum chemistry and hematology
- Urinalysis
- Urine pregnancy test (for women of childbearing potential only)
- Cancer screening should be conducted per the current American Cancer Society Guidelines for the Early Detection of Cancer. Testing should also include: pap smear and mammogram if not performed within past 12 months (females only); chest X-ray or chest CT scan (if the subject has a previous history of tobacco use, a CT scan will be performed instead of X-ray) within 3 months prior to study entry; PSA within past 3 months (males only);[†] for subjects ≥ 50 years old, colonoscopy within past 10 years; for subjects with family history of colon cancer in any first degree relative, colonoscopy within past 12 months.
- Viral screening – HIV, Anti-Human T-Cell Lymphotropic Virus (HTLV), Positive Hepatitis B or C as determined by Hepatitis B core antibody (HBcAb), antibody to Hepatitis B antigen (IgG and IgM; HBsAb), Hepatitis B surface antigen (HBsAg) and Hepatitis C antibodies (Anti-HCV), at Screening
- Retinal Fundoscopy – in cases where fundoscopy alone is deemed insufficient to rule out exclusionary conditions (see exclusion criterion # 12), fluorescein angiography may be conducted
- ***Following medication washout (if applicable) and within 14 days prior to injection.*** Subjects will keep a Daily Pain and Sleep Interference Diary for 7 days. They will be asked to rate their 24-hour average daily pain intensity score using an 11 point numerical scale with 0 mm = no pain – 10 0 mmworst possible pain, and to evaluate how much their pain interferes with sleep (also using an 11 point numerical rating scale from 0 (did not interfere with sleep) to 10 (completely interfered with sleep; patient was not able to sleep due to pain). The subject must record at least five assessments of the 24-hour average daily pain intensity score during the seven-day period. The mean 24-hour scores at Screening will represent the baseline reference value. In case less than five assessments are recorded, a new Daily Pain and Sleep Interference Diary will be provided and the Day 0 visit will be rescheduled to allow completion of the Diary. The average pain score of the Daily Pain and Sleep Interference Diary must be ≥ 4 with a standard deviation ≤ 2 in order to be eligible for study participation.

[†] subjects can participate in the study if PSA is elevated, but cancer can be excluded

3.4.4. PROHIBITED CONCOMITANT MEDICATIONS

3.4.4.1. MEDICATION THAT MAY INTERFERE WITH VM202 BIOACTIVITY

COX-1 and COX-2 inhibiting drugs will interfere with the bioactivity of VM202, and are therefore prohibited from use during the study. Other than the maximal 81 mg daily dose of aspirin (acetylsalicylic acid), subjects must agree to not take any of these drugs until completion of the 9 month follow-up visit. The patient needs to be advised that common over the counter medications excluded include: Bayer (> 81mg), Excedrin, Aleve, Advil (motrin, ibuprofen). A full list of the excluded medications, including the washout period, can be found in [Appendix 3](#).

3.4.4.2. MEDICATIONS THAT MAY INTERFERE WITH ASSESSMENT OF VM202 EFFECT ON PAIN

Subjects may not take new drugs for DPN symptoms during the study and must be on the same medication for at least one month prior to screening. However, subjects are allowed to stop the existing medication during the study.

Subjects must discontinue use of all opioid drugs fourteen days prior to the completion of the Daily Pain and Sleep Interference Diary and agree to remain off of these medications until completion of the 9 month follow-up visit.

3.4.4.3. SCREEN FAILURES

Subjects not meeting all study entry criteria will be designated as a screen failures. End of study procedures will not be performed for these subjects, but their reason for discontinuation will be recorded on Screening Log. Screen failures will be replaced.

3.4.5. TREATMENT AUTHORIZATION

After providing written informed consent, potential study participants will undergo Screening assessments. The site will complete a Treatment Authorization Form (TAF) for subjects determined to be eligible for study participation. The TAF includes the subject identification number, demographic information (gender, date of birth) and indication that the subject meets all inclusion and exclusion criteria. The completed TAF and completed Daily Pain and Sleep Interference Diary will be faxed to the Sponsor or its designee. The Sponsor or its designee will confirm whether the subject can be treated, and return the TAF to the investigational site and a copy to the drug depot. Upon receipt, the Investigator will schedule the subject to undergo the study treatment. Note: adherence to this process is mandatory to track enrollment and to assure proper randomization.

3.4.6. RANDOMIZATION AND BLINDING

A randomization schedule with subjects allocated to high dose, low dose or control in a 2:2:1 ratio will be sent to a centralized drug depot, which will prepare individual kits that contain the appropriate treatment based on the randomization schedule. When a site identifies a subject and treatment authorization is granted, the Sponsor or its designee will notify the drug depot.

The drug depot will:

1. Ship the next kit in sequence to the study pharmacist at the site, labeled with the subject identification number.
2. Record which kit was assigned to which site/subject and the date.
3. Include in the kit, a sealed envelope that identifies the subject identification number on the outside and the assigned treatment inside, to be opened by the Investigator or designee only in the case of a medical emergency.
4. Send another sealed envelope to the Sponsor with the subject identification number on the outside and the assigned treatment inside, to be opened by the Sponsor or designee only in the case of a medical emergency.

Blinding will be achieved by having the study medication (VM202) prepared by the study pharmacist. Reconstituted VM202 is indistinguishable from saline solution. The site pharmacist prepares the vials according to the instructions in the kit (which vials to reconstitute with water for injection [WFI]). The drug depot, site pharmacist and select individuals at [REDACTED] (but not including study monitors and study manager) will be unblinded to the treatment assignments. The subject and study personnel, including core lab, principal investigator, co-investigators and study coordinators, will remain blinded until all data has been entered into the database and the database is locked.

IN CASE OF EMERGENCY ONLY, i.e. SERIOUS ADVERSE EVENT (SAE) AND ONLY WHEN THIS INFORMATION INFLUENCES THE SUBJECT'S MANAGEMENT, the Investigator may open the sealed envelope to unblind the study medication assignment.

For each opened envelope, the Investigator will provide the name of the person who opened the envelope, reason, date, and signature on the envelope. At the end of the study, all (opened and unopened) envelopes will be returned to the Sponsor.

3.4.7. DAY -7 (-7 DAYS)

- Daily Pain and Sleep Interference Diary

3.4.8. DAY 0 – 1ST INJECTIONS

3.4.8.1. PRE-INJECTION (WITHIN 4 HRS PRIOR TO INJECTIONS)

- Concomitant Medications
- Vital Signs
- VAS
- Brief Pain Inventory for Diabetic Neuropathy (BPI-DPN)
- Serum Chemistry and Hematology
- Serum HGF
- Copies of VM202 in whole blood
- Skin biopsy

3.4.8.2. 1ST DOSE OF VM202 OR PLACEBO

Thirty-two (32) IM injections of randomly assigned study medication in each calf for a total of 64 injections will be administered per patient.

3.4.8.3. POST-INJECTION

- Vital Signs
- Copies of VM202 in whole blood (2 hours \pm 1 hour post injection)
- Injection site assessment
- Adverse event assessment

3.4.9. DAY 14 \pm 1 DAY – 2ND INJECTIONS

3.4.9.1. PRE-INJECTION (WITHIN 4 HOURS PRIOR TO THE INJECTIONS)

- Concomitant Medications
- Vital Signs
- Serum HGF
- Copies of VM202 in whole blood
- Injection site assessment
- Adverse event assessment

3.4.9.2. 2ND DOSE OF VM202 OR PLACEBO

Thirty-two (32) IM injections of randomly assigned study medication in each calf for a total of 64 injections will be administered per patient.

3.4.9.3. POST-INJECTION

- Vital Signs
- Copies of VM202 in whole blood (2 hours \pm 1 hour post injection)
- Injection site assessment
- Adverse event assessment

3.4.10. DAY 21 \pm 3 DAYS

- Concomitant Medications
- Vital Signs
- Copies of VM202 in whole blood
- Injection site assessment
- Adverse event assessment

3.4.11. DAY 30 \pm 3 DAYS

- Concomitant Medications
- Vital Signs
- VAS
- Patient's Global Impression of Change (PGIC)

- Brief Pain Inventory for Diabetic Neuropathy (BPI-DPN)
- Serum Chemistry and Hematology
- Serum HGF
- Copies of VM202 in whole blood
- Injection site assessment
- Adverse event assessment

3.4.12. DAY 60±3 DAYS

- Concomitant Medications
- Vital Signs
- VAS
- Patient's Global Impression of Change (PGIC)
- Brief Pain Inventory for Diabetic Neuropathy (BPI-DPN)
- Serum HGF
- Copies of VM202 in whole blood
- Injection site assessment
- Adverse event assessment

3.4.13. DAY 90±7 DAYS

- Concomitant Medications
- Vital Signs
- VAS
- Daily Pain and Sleep Interference Diary – to be completed within 14 days prior to the visit
- Patient's Global Impression of Change (PGIC)
- Brief Pain Inventory for Diabetic Neuropathy (BPI-DPN)
- Serum Chemistry and Hematology
- HbA1c
- Serum HGF
- Copies of VM202 in whole blood
- Adverse event assessment

3.4.14. 6 MONTHS±1 MONTH

- Concomitant Medications
- Vital Signs
- VAS
- Michigan Neuropathy Screening Instrument (MNSI)
- Daily Pain and Sleep Interference Diary – to be completed within 14 days prior to the visit
- Patient's Global Impression of Change (PGIC)
- Brief Pain Inventory for Diabetic Neuropathy (BPI-DPN)
- Brief Peripheral Neuropathy Screening (BPNS)
- HbA1c
- Skin biopsy

- Adverse event assessment

3.4.15. 9 MONTHS ± 1 MONTH

- Retinal fundoscopy
- Concomitant Medications
- Vital Signs
- VAS
- Michigan Neuropathy Screening Instrument (MNSI)
- Daily Pain and Sleep Interference Diary – completed within 14 days prior to visit
- Patient's Global Impression of Change (PGIC)
- Brief Pain Inventory for Diabetic Neuropathy (BPI-DPN)
- Serum Chemistry and Hematology
- HbA1c
- Adverse event assessment

3.5. STUDY COMPLETION

3.5.1. COMPLETED SUBJECTS

Each subject in the study will be considered completed when all assessments through 9 months have been performed in accordance with the study protocol.

3.5.2. DISCONTINUED SUBJECTS

Any subject may voluntarily discontinue the study at any time without prejudice. The investigator may discontinue a subject from the study at any time if (s)he considers that remaining in the study compromises the subject's health or the subject is not sufficiently cooperative. In either event, reason(s) for discontinuation should be recorded on the CRF.

Possible reasons for study discontinuation include the following:

- Adverse events (AEs) necessitating discontinuation from the study (pre-treatment).
- The subject is lost to follow-up.
- Subject decision (specify).
- Investigator decision (specify).
- Other reason (specify).

The reasons for any subject discontinuation will be recorded on the study completion form of the CRF.

Additional subjects may be enrolled if subjects discontinue prior to the 90 day visit in order to achieve a 100 patient dataset with 90 day data.

Subjects discontinued for AE(s) will be followed-up after subject's discontinuation until the event is resolved or considered medically stable by the investigator.

Subjects that withdraw prior to study completion will undergo the following if possible:

- Retinal Fundoscopy
- Concomitant Medications
- Serum Chemistry and Hematology
- HbA1c
- Vital Signs
- Serum HGF if discontinued prior to Day 90
- Copies of VM202 in whole blood if discontinued prior to Day 90
- Injection site reaction assessment if discontinued prior to Day 60
- Adverse Events

In case of a subject lost-to-follow-up, the investigator must do his/her best to contact the subject (by phone or letter) at least twice. If no response is obtained from the subject, the investigator is encouraged to contact one of the subject's relatives or his/her general practitioner. Documentation of these contacts must be recorded in the subject medical chart. It can be, for instance, the acknowledgement of receipt of a letter sent to the subject.

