5.3. REPORTING/RECORDING OF AEs

Throughout the course of the study, all efforts will be made by the investigator to remain alert to possible AEs. The first concern will be the safety of the subject, and for providing appropriate medical intervention. The period of observation for collection of AEs starts during the first intramuscular injection procedure (Day 0) until the 9 month follow-up visit. Any AE should be recorded on the appropriate CRF page(s).

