6.4. SUBJECT CATEGORIZATION

Screen Failure - Any subject who was consented and entered into the Screening process appropriately, but subsequently did not meet the entry criteria in order to be treated. Subjects who fail screening will not be followed for safety or efficacy assessment, and no other study procedures will be performed. Screen failures will be replaced.

Evaluable Subject - Any subject who received the study drug.

Lost to follow-up - A subject deemed to be lost to follow-up is any subject who received treatment, but who does not complete scheduled study visits. This includes those subjects who withdraw consent and refuse further study participation and all attempts to contact the subject are deemed unsuccessful.

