7. SUBJECT DISPOSITION

Subject disposition information will be summarized for all subjects by dose cohort. Summaries will include the number of subjects:

- enrolled
- in each analysis population
- who received all planned doses of VM202
- who completed each scheduled visit
- who completed the study
- who discontinued the study early, and their primary reason for early discontinuation.

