11.1.1. Handling Missing Data

For ITT population, the analyses with imputation for missing data will be performed for the primary efficacy endpoint (pain score change from baseline to 6 months). For subjects without the primary efficacy endpoint, the following imputation methods will be considered:

- For subjects with an early drop-out reason not related to death or AEs, the last available value (LOCF) of the subject will be used for the missing 6-month value. For early discontinued subjects due to AEs, the maximum value of all available 6-month pain score will be imputed for the missing 6-month value. For early discontinued subjects due to death, no imputation will be performed and therefore will not be included in the 6-month analyses if they are discontinued prior to the 6-month visit.

No imputation for missing values will be performed for other variables.

11.2. Outcome of at least 50% Reduction in Average Pain Score from Baseline to 6-Month

The percent reduction in the average pain score (determined by the 7-Day Daily Pain and Sleep Interference Diary) from baseline to 6-month follow-up will be calculated for each subject as follows:

$$\% \text{ reduction} = (\text{Baseline Pain Score} - \text{6-month Pain Score}) \div \text{Baseline Pain Score} \times 100\%.$$

The percentage of subjects with at least 50% reduction in pain from baseline to the 6-month follow-up and the corresponding 95% confidence intervals based on the binomial distribution will be calculated for each study group. Fisher's exact test will be used to compare the percentage of subjects with at least 50% reduction in pain among the three study groups. The comparison between the placebo group and each of the two VM202 group will also be performed by Fisher's exact test. The 95% confidence interval of the difference between placebo and each of the two VM202 group in the percentage of subjects with at least 50% reduction will be derived by the two-sample normal distribution.

The percentage of subjects with at least 20%, 30%, 40%, 60%, 70%, and 80% reduction in pain and the corresponding 95% confidence intervals based on the binomial distribution will also be provided.

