12.3. Adverse Events

All adverse event summaries will be restricted to Treatment Emergent Adverse Events (TEAE), which are defined as those AEs that occurred after dosing and those existing AEs that worsened during the study. Verbatim terms on case report forms will be mapped to preferred terms. It should be noted that only the AEs after the first round of injection will be collected during the study.

The adverse event summaries will be displayed by treatment arm. The number of subjects experiencing a particular event, the percentage of subjects experiencing the event, and the total number of events will be presented. The following summaries will be created:

- TEAE by preferred term;
- TEAE by preferred term and maximum severity. At each level of subject summarization, a subject is classified according to the highest severity if the subject

reported one or more events. AEs with missing severity will be considered severe for this summary;

- TEAE by preferred term and closest relationship to study drug (Related/Not Related). At each level of subject summarization, a subject is classified according to the closest relationship if the subject reported one or more events. AEs with a missing relationship will be considered related for this summary; events classified as ‘possibly’, ‘probably’ or ‘definitely’ will be considered ‘related’.
- Serious TEAEs by preferred term.

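### The adverse-event discontinuation reason is limited to pre-treatment and lost to follow-up is defined too broadly, so AE withdrawals after dosing may be coded inconsistently in the disposition table and the imputed ITT analysis

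*Protocol*

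**What the plan says.** Protocol 3.5.2 introduces its reasons with "Possible reasons for study discontinuation include the following". The first is "Adverse events (AEs) necessitating discontinuation from the study (pre-treatment". The others are lost to follow-up, subject decision, investigator decision and other reason, the last three each with a request to specify. Death is not listed. The reason goes on the study completion form. Further down, the section says "Subjects discontinued for AE(s) will be followed-up after" they leave, this time with no pre-treatment limit.

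Protocol 6.4 states: "A subject deemed to be lost to follow-up is any subject who received treatment, but who does not complete scheduled study visits". Its next sentence brings in subjects who withdraw consent, refuse further participation and cannot be reached.

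On AE collection, Protocol 5.3 says "The period of observation for collection of AEs starts during the first intramuscular injection procedure (Day 0", and SAP 12.3 says "It should be noted that only the AEs after the first round of injection will be collected during the study". Protocol 4.1.1 treats new findings before the first dose as medical history, not as AEs.

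Two parts of the SAP use the reason. SAP 7 counts subjects "who discontinued the study early, and their primary reason for early discontinuation". SAP 11.1.1 chooses the imputation by it: "For early discontinued subjects due to AEs, the maximum value of all available 6-month pain score will be imputed"; for deaths nothing is imputed; for reasons unrelated to death or AEs the last available value is carried forward (LOCF).

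**The concern.** The recorded reason has to do two jobs, and the listed categories do not clearly support either.

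The first is safety reporting. Safety is the primary objective (SAP 2.1). Protocol 6.3.3 says AEs leading to treatment discontinuation will be described, but neither SAP 12.3 nor SAP Appendix A lists a table for them. The disposition table is then the one planned summary that would count subjects who left because of an AE. If sites spread those subjects over other categories, the count is too low.

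The second is the imputed ITT analysis of the 6-month diary score (SAP Appendix A, Table 5.3). It is the only planned analysis of that endpoint that gives dropouts a 6-month value. If a treated AE withdrawal is coded under another reason, LOCF may replace the maximum score. That makes the arm that lost the subject look better.

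**Working it through.** The plan states no figure for withdrawals, so the check is mainly a comparison of texts, followed by an illustration of size.

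**Texts side by side**

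1. *AE reason against AE window.* If pre-treatment means before the first injection, the category can hold no protocol-defined AE: collection starts with that injection (Protocol 5.3, SAP 12.3) and earlier findings are medical history (Protocol 4.1.1).
2. *AE reason against the rest of 3.5.2.* The follow-up rule for subjects discontinued for AEs has no such limit. The two statements need reconciling.
3. *Protocol 6.4 against 3.5.2.* The first sentence of 6.4 fits a treated subject who leaves for any reason, so it overlaps AE, subject decision and investigator decision.
4. *Categories against SAP 11.1.1.* The SAP has three branches: AE, death, anything else. The protocol list has no death and no clear post-dose AE, and 11.1.1 names no field. A subject recorded under subject decision, with an AE in the specify text, is not clearly in either branch: LOCF is for reasons not related to AEs, while the maximum is for discontinuation due to AEs.

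**What LOCF would carry forward**

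The diary is scheduled at Screening, Day 90, 6 months and 9 months, and not at early withdrawal (Protocol 3.5.2, Appendix 1). For a subject leaving before Day 90, the last available value is the baseline score, so the imputed change is 0. This assumes that baseline may be carried forward, which SAP 11.1.1 does not exclude.

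**Size**

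Let k be the number of AE withdrawals given LOCF instead of the maximum, g the maximum minus the carried value, and n the arm size. The shift in the arm's imputed ITT mean is k × g / n.

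- Arm sizes are 40, 40 and 20 (SAP 4).
- Eligibility requires a baseline diary mean of at least 4 on the 0–10 scale. Before Day 90, g is therefore at most 10 − 4 = 6.
- The lower value g = 2 is an assumption, as is k.

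| k | Arm | g = 2 | g = 4 | g = 6 |
|---|---|---|---|---|
| 1 | active, n=40 | 0.05 | 0.10 | 0.15 |
| 1 | placebo, n=20 | 0.10 | 0.20 | 0.30 |
| 2 | active, n=40 | 0.10 | 0.20 | 0.30 |
| 2 | placebo, n=20 | 0.20 | 0.40 | 0.60 |

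The SAP 4 planning difference serves as a yardstick. A two-sided t-test at 0.025 with SD 25 mm and 40 against 20 subjects gives 79.7% power at 21.5 mm, in line with the stated 80%. If 10 mm equals one diary point (an assumption), 21.5 mm is 2.15 points. One miscoded subject then amounts to 0.05/2.15 = 2.3% to 0.15/2.15 = 7.0% of that difference in an active arm, and 4.7% to 14.0% in placebo.

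**The case against.** A reader might infer that AE withdrawals will not be counted at all and that the AE imputation rule is bound to reach the wrong subjects. The documents do not support that.

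- The reason list is open, has specify fields, and sits beside a provision for subjects discontinued for AEs. Post-dose AEs are recorded through 9 months whatever reason is ticked. A death fits other reason and is reported as an SAE.
- Pre-treatment need not mean before Day 0. The protocol uses the same word for the serum HGF sample before the Day 14 injection. On that reading the category covers an AE after the first injection that prevents the second.
- A reader might also infer from Protocol 6.4 that every treated non-completer, including anyone who withdraws consent, is lost to follow-up. Its second sentence ties consent withdrawal to failed contact, and 3.5.2 describes lost to follow-up as a contact failure.
- SAP 11.1.1 refers to neither the 6.4 label nor the 3.5.2 list, and the completion form is not among the documents.
- The qualifier may reflect a wish to keep treated subjects in follow-up.

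Most of this stands, and it turns certain misclassification into a risk of inconsistent coding. It does not remove the conflict. Even on the Day 14 reading, no listed AE reason covers the period after the second injection. Specify fields leave the classification to judgement across up to twenty sites. If the qualifier does express an intention to retain treated subjects, the protocol should say so.

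**Conclusion.** The point holds as an inconsistency in wording that affects two outputs. The AE reason in Protocol 3.5.2 conflicts with the AE collection window, with its own section and with what SAP 11.1.1 needs; the first sentence of Protocol 6.4 overlaps the other reasons. The result may be an understated count of AE withdrawals in the disposition table, and LOCF in place of the maximum score in the secondary imputed ITT analysis.

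The primary analysis is unaffected: the Efficacy Analysis Group requires the 6-month assessment, so nothing is imputed there. The SAP also treats its p-values as descriptive.

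The shift of 0.05–0.15 points (active) or 0.10–0.30 points (placebo) per miscoded subject rests on an assumed gap of 2 to 6 points. The upper end applies to departure before Day 90. The figures show the arithmetic and are not an estimate of expected bias. The correction is worth making because it is cheap and closes a route to under-reporting in a trial whose primary objective is safety.

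**What to change.** - **Protocol 3.5.2 and the study completion form:** delete the pre-treatment qualifier so that the AE reason covers the post-dose period, and add death as a reason.
- **Protocol 6.4:** limit lost to follow-up to subjects who cannot be contacted, and place other consent withdrawals under subject decision.
- **One primary reason:** keep a single primary reason per subject, since that is what SAP 7 tabulates. Recording AE whenever an AE merely contributed would conflict with SAP 7 and would give the maximum score to subjects who left mainly for something else.
- **SAP 7 and 11.1.1:** name that CRF field as the source of both the disposition table and the imputation branch.

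The cost is protocol, CRF and SAP wording. No visit or procedure is added, no stated figure changes, and the change concerns how a departure is recorded, not who should leave the study.

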3.3. SUBJECT POPULATION

One-hundred (100) evaluable subjects with DPN meeting the following study entry criteria will be enrolled.

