6.2. ANALYSIS POPULATION

Efficacy Analysis Population – Subjects that received all injections of the correct dose of study drug medication based on randomization schedule and have completed the 6-month assessment; subjects must not have any protocol violation or major deviation which will be determined in a blinded review before database lock for data analyses.

Safety Analysis Population – Subjects that have received any injections

Intent to Treat (ITT) Population – All randomized patients

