6.3.1. PRIMARY ENDPOINT

The primary study endpoint is the change in average 24-hour pain score from baseline to the 6-month follow-up. The average pain scores will be obtained from the Daily Pain and Sleep Interference Diary (recorded daily by the patient for 7 days prior to the first round of injections and again, for 7 days before the 6 month follow-up). The difference in the mean change in average 24 hour pain score between the two treatment groups and the placebo arm will be evaluated to determine the treatment effect.

The primary analysis will be conducted in the Efficacy Analysis Group. A secondary analysis will be conducted in the ITT group, and further analyses conducted as necessary to explore any inconsistency between the two results.

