4. SAMPLE SIZE JUSTIFICATION

The sample size for this Phase 2 study was chosen to estimate effect sizes and variability for a pivotal study. Based on the 12 subjects in the Phase I study (Protocol VMDN-001), the overall mean VAS reduction from baseline to 6 months is about 23 mm with a standard deviation of about 25 mm.

This Phase II study has two VM202 dose groups (16 mg and 32 mg) and a placebo group. The study goal is to identify any difference in mean reduction in pain as measured by the Daily Pain and Sleep Interference Diary between each of the two VM202 groups against the placebo group. Based on the two-sided two-sample t-test with a significance level of 0.025 (per the Bonferroni adjustment for multiple comparisons) and an assumption of a standard deviation of 25 mm, a sample size of 40 subjects versus 20 subjects has a statistical power of 80% to detect a mean difference of 21.5 mm, a statistical power of 70% to detect a mean difference 19.5 mm, and a statistical power of 60% to detect a mean difference of 17.5 mm. Therefore, the sample size for Protocol VMDN-002 is determined to be 40 subjects in the VM202 16 mg group, 40 subjects in the VM202 32 mg group, and 20 subjects in the placebo group.

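### The optional top-up stops at Day 90, but the SAP's 80% power needs 40 v 20 subjects in the 6-month Efficacy Analysis Group, so the figure holds only if nobody is lost or excluded

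*Protocol*

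**What the plan says.** **Top-up.** Protocol 3.5.2 leaves the sponsor free to enrol more people when "subjects discontinue prior to the 90 day visit in order to achieve a 100 patient dataset with 90 day data". The wording is permissive and refers to a total, not to arms.

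**Endpoint and analysis set.** Protocol 6.3.1: "The primary study endpoint is the change in average 24-hour pain score from baseline to the 6-month follow-up". The same section adds: "The primary analysis will be conducted in the Efficacy Analysis Group". Under Protocol 6.2, members of that group must have received all injections of the correct dose and "have completed the 6-month assessment; subjects must not have any protocol violation or major deviation". SAP section 6 defines the group in the same way.

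**The number 100.** The synopsis gives 100 as the number randomised 2:2:1. Protocol 3.3 says: "One-hundred (100) evaluable subjects with DPN meeting the following study entry criteria will be enrolled". Protocol 6.4 defines the term: "Evaluable Subject - Any subject who received the study drug". Protocol 3.5.2 makes 100 the number with Day 90 data.

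**Power.** SAP section 4, using a two-sided t-test at 0.025 and an SD of 25 mm, states that "a sample size of 40 subjects versus 20 subjects has a statistical power of 80% to detect a mean difference of 21.5 mm". It then sets the sample size at 40, 40 and 20, with no allowance for loss.

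**Missing data.** SAP 11.1.1 imputes the 6-month score only in the ITT population. It carries the last value forward for drop-outs unrelated to AEs or death, and uses the largest observed 6-month score for AE drop-outs. Deaths are not imputed.

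**The concern.** A subject who leaves between Day 90 and 6 months counts towards the Day 90 target, is not replaced, and cannot enter the primary analysis. The same is true of a subject excluded at the blinded review for a violation or major deviation. No other provision covers these losses. The early-withdrawal assessments (Protocol 3.5.2 and Appendix 1) include no diary, and imputation does not reach the primary analysis set.

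The plan therefore uses 100 in three senses (randomised, dosed, with Day 90 data). None of them is the count on which the 40 v 20 power rests. If any top-up is made, the number randomised exceeds 100, so the synopsis and 3.5.2 cannot both describe the final count. The sponsor could meet its Day 90 target in full and still have fewer than 40 v 20 at the primary analysis, while the SAP continued to quote 80%.

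**Working it through.** **Inputs from SAP section 4:** two-sided alpha 0.025 per comparison, SD 25 mm, difference 21.5 mm, 40 active v 20 placebo.

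**Formula.** SE = 25 × √(1/n₁ + 1/n₂). Non-centrality = difference / SE. Degrees of freedom = n₁ + n₂ − 2. Power is the probability that a non-central t exceeds the critical value t(0.9875, df).

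**Reproducing the stated figure.** SE = 25 × √(1/40 + 1/20) = 6.847. Non-centrality = 21.5 / 6.847 = 3.140. With df = 58 the critical value is 2.301, and power is 79.7%. The SAP's other two points also reproduce: 70.7% at 19.5 mm (stated 70%) and 60.2% at 17.5 mm (stated 60%). The SAP's arithmetic is sound for 40 v 20 analysed.

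**Same formula with fewer subjects in the Efficacy Analysis Group** (21.5 mm difference, equal proportional loss in both arms; the loss rates are assumptions):

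| Lost or excluded | Analysed | SE (mm) | Non-centrality | Power |
|---|---|---|---|---|
| 0% | 40 v 20 | 6.847 | 3.140 | 79.7% |
| 5% | 38 v 19 | 7.024 | 3.061 | 77.3% |
| 10% | 36 v 18 | 7.217 | 2.979 | 74.7% |
| 15% | 34 v 17 | 7.426 | 2.895 | 71.9% |
| 20% | 32 v 16 | 7.655 | 2.809 | 68.8% |

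Equivalently, the difference detectable with 80% power rises from 21.6 mm with no loss to 22.8 mm at 10% and 24.3 mm at 20%.

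**Does a top-up restore the arms?** Protocol 3.4.6 tells the depot to "Ship the next kit in sequence to the study pharmacist at the site" from a 2:2:1 schedule, so on average 1 in 5 top-ups is placebo. If eight losses fall in proportion to allocation, 8 × 1/5 = 1.6 are placebo and eight top-ups return 8 × 1/5 = 1.6, so no deficit is expected. A deficit appears only with differential drop-out. For example, with 4 placebo and 4 active losses, 20 − 4 + 1.6 = 17.6 placebo subjects remain on average, but this assumes 4/20 = 20% loss on placebo against 4/80 = 5% on VM202. Nothing in the documents supports such a difference.

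**The case against.** **Day 90 has a function.** The diary is completed at screening, Day 90, 6 months and 9 months, so Day 90 gives the first post-baseline value of the primary instrument. A subject with Day 90 data who later leaves for a reason other than an AE or death has a post-baseline value to carry forward. A reader might infer that the cut-off is arbitrary, or that such subjects are lost to every analysis. Neither follows, because they can contribute to the imputed ITT analysis. That analysis is secondary, however, and the documents do not give this as the reason for the rule.

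**Power is not the main rationale.** SAP section 4 says the size was chosen to estimate effect sizes and variability for a pivotal study. SAP section 5 treats p-values as descriptive, and the SAP's primary objective is safety. The 80% is one of three power points, and none is named as a requirement. This stands, and it limits the weight of the point. But the SAP does justify 40/40/20 by power, and fewer 6-month subjects also reduce precision for its estimation aim.

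**Losses may be small.** In the earlier DPN study of this drug (Protocol 1.6.3), pain results are reported for 12 of 12 subjects at 6 and at 12 months. In the ongoing critical limb ischaemia study (Protocol 1.6.2), 2 of 33 had left early, with follow-up incomplete. These samples are too small to exclude 10%, but they give no reason to expect 20% between Day 90 and 6 months. Nor do they address exclusions for violations.

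**Stronger readings to avoid.** A reader might infer that the rule guarantees 100 at Day 90; it says only that subjects may be added. A reader might infer that the placebo arm will end near 17.6, but that needs the differential loss shown above. A reader might also infer that the top-up should simply move to 6 months. That would mean longer and larger enrolment. It would not restore 40/40/20 under sequential kit allocation, and a 6-month diary does not by itself confer membership of the Efficacy Analysis Group.

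**Conclusion.** The point holds as a planning gap and an inconsistency in what the 100 means. It is not an arithmetic error, and it does not show that the trial is underpowered. The stated 80% is correct for 40 v 20 analysed at 6 months without violations, and the plan contains nothing that delivers that set. Power at 21.5 mm is about 77% at 5% loss, 75% at 10% and 69% at 20%. These figures rest on the SAP's own planning test, its SD of 25 mm and equal proportional loss across arms. The actual size of the shortfall cannot be fixed from the documents, because they give no planning loss rate. In a Phase II trial with descriptive p-values the consequence is moderate: a stated power that no realised dataset is likely to match exactly, and some loss of precision.

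**What to change.** 1. In Protocol 3.3 and 3.5.2 use one definition of the 100, matching the synopsis: 100 subjects randomised, 40/40/20. Remove the Day 90 dataset target and the word evaluable from the enrolment target, or reconcile both with that definition. If the option to add subjects is kept, say that they are additional to the 100.
2. In SAP section 4 state that the 80% applies to 40 v 20 in the Efficacy Analysis Group at 6 months. Add power over a stated range of assumed loss or exclusion, for example the 5%, 10% and 20% rows above, and note that the range is assumed.

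The cost is wording in two documents and a slightly less favourable stated power. No subjects, visits or procedures are added. Keeping the full 40 v 20 by enrolling more would be a different and dearer choice: at 10% loss it needs 40/0.9, rounded up to 45, per active arm and 20/0.9, rounded up to 23, on placebo. This point does not call for it.
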